### **11.3.1 Variables and Criteria Defining Abnormality**

Clinical laboratory tests performed by central laboratory service provider are listed below.

**Table 7. Clinical Laboratory Tests**

Category	Test Name
Hematology	Hematocrit (Hct) Hemoglobin (Hb) White Blood Cells/Leukocytes Platelet Count/Thrombocytes
Diff. Automatic	Neutrophils (absolute count) Lymphocytes (absolute count)
Enzymes	AST (GOT) ALT (GPT) Alkaline Phosphatase (ALP) Creatine Kinase (CPK) Gamma-glutamyl transferase (GGT/γ-GT)
Electrolytes	Calcium Sodium Potassium
Substrates	Glucose Creatinine Bilirubin Total (TBL) Bilirubin Direct (if total is elevated) Albumin C-Reactive Protein (CRP) (high sensitivity) Cholesterol, total a Triglycerides a LDL-Cholesterol a HDL-Cholesterol a
Urine	UACR

a. To be done at screening only.

### 11.3.2 Statistical Methods

#### Analysis of Continuous Laboratory Parameters

Analyses of laboratory data will be presented based on the National Cancer Institute Common Toxicity Criteria for Adverse Event (NCI CTCAE) scale. Change from Baseline to each scheduled visit and to the final value in continuous laboratory parameters will be summarized with the mean, standard deviation and median. The Baseline and visit/final value means will also be presented for subjects who have both the Baseline and

visit/final values (see Section 6.0 for the definition of Baseline and final values). If there are multiple post-baseline measurements on the same day, the average value will be used.

### **Shift Tables**

Shift tables for changes from Baseline according to the normal range will be provided for each hematology and clinical chemistry parameter. Shifts from Baseline to the following endpoints will be considered: minimum value, maximum value and final value.

Categories of "low or normal" and "high or normal" will be included at Baseline in addition to the categories of "low," "normal," "high" and "missing." If there are multiple measurements on the same day, the last value will be used.

### **Potentially Clinically Important Laboratory Values**

Frequencies and percentages of subjects with post Baseline lab values meeting the following criteria will be summarized.

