Fumaderm® is a widely prescribed systemic therapy for moderate to severe psoriasis, although registered for this indication in Germany only, a high proportion of patients treated with FUMADERM® experience a significant improvement in their psoriatic skin disease over a period of about 3 months of treatment.

The safety profile of FUMADERM® is well characterized. Gastrointestinal complaints (in up to 60% of subjects especially in the initial weeks of therapy) and flush are the most common side effects of fumaric acid esters. Gastrointestinal tract symptoms include diarrhea, increased frequency of stools, nausea, and abdominal cramps. The symptoms of flush are highly variable and range from a brief feeling of warmth to reddening of the face

lasting for several hours. Leukocytopenia, lymphocytopenia, and eosinophilia are common side effects of fumaric acid esters. The other adverse events reported in association with FUMADERM® remain uncommon to very rare: acute lymphocytic leukemia, increase in liver function tests, Fanconi syndrome, opportunistic infection increases including isolated cases of progressive multifocal encephalopathy.

There is no known association of FUMADERM® with malignancy.

There are no studies on the use of fumaric acid esters during pregnancy or in nursing women. Toxicology studies have shown that fumaric acid esters have neither teratogenic nor mutagenic potential.

The well codified dosing schedule for FUMADERM®, based on individual efficacy and safety response and the long experience in clinical practice since its commercialization guarantees an acceptable risk-benefit balance. Pregnancy and breastfeeding as well as severe liver, kidney and gastrointestinal diseases are contraindication to Fumaderm®.

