**Table 3. Clinical Laboratory Tests**

Category	Test Name
Hematology	Hematocrit (Hct) Hemoglobin (Hb) Red Blood Cell Count/Erythrocytes White Blood Cells/Leukocytes Platelet Count/Thrombocytes
Diff. Automatic	Neutrophils (absolute count) Eosinophils (absolute count) Basophils (absolute count) Monocytes (absolute count) Lymphocytes (absolute count)
Diff. Manual (if Diff Automatic is abnormal)	Neutrophils, bands (Stabs) Neutrophils, polymorphonuclear (PMN) Eosinophils Basophils Monocytes Lymphocytes
Enzymes	AST(GOT) ALT(GPT) Alkaline Phosphatase (AP) Creatine Kinase (CK) CK-MB, only if CK is elevated Gamma-glutamyl transferase (GGT/γ-GT)
Electrolytes	Calcium Sodium Potassium Chloride Bicarbonate
Substrates	Glucose BUN Creatinine Bilirubin Total Bilirubin Direct (if total is elevated) Bilirubin Indirect (if total is elevated) Albumin C-Reactive Protein (CRP) (high sensitivity) Cholesterol, total a Triglycerides a LDL-Cholesterol a HDL-Cholesterol a FSH b

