#### **5.4.1.1 Discontinuation of Subjects on FUMADERM®**

Subjects that are randomized to FUMADERM® INITIAL or FUMADERM® should be discontinued if any of the following occur:

1. A pronounced decrease in WBC count of > 50% between 2 visits or an absolute WBC count below 3,000/ $\mu$ l.

2. A lymphocyte count below 500/ $\mu$ l.
3. A lymphocyte count below 700/ $\mu$ l that persists 4 weeks after having reduced the dose of FUMADERM® INITIAL or FUMADERM® by half.
4. A Platelet count < 100 000/ $\mu$ l.
5. A diagnosis of progressive multifocal leukoencephalopathy.
6. An opportunistic infection, including but not limited to visceral herpes simplex, disseminated candidiasis, aspergillus colonization, acute pneumocystis carinii pneumonia or visceral CMV infection.
7. An increase in creatinine level above normal according to central laboratory normal range.
8. Severe rash/flush that does not resolve with continued treatment.
9. Major gastro-intestinal complaints that do not resolve with continued treatment in spite of dose reduction.

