## **8.2 Determination of Sample Size**

Using a two-sided Chi squared test at level of significance 5%, the sample size of 110 (2 × 55) subjects will provide 94% power assuming response rates of the primary endpoint (PASI90 at Week 24) of 70% for risankizumab and 35% for FUMADERM®.

These assumptions are in line with what has been observed in recent studies for Risankizumab (63/83 (75.9%) at Week 24) and FUMADERM® 61/273 (22.3%) of the subjects achieved PASI 90 at Week 16 in the FUMADERM® arm in the BRIDGE trial.

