**Table 9. Criteria for Potentially Clinically Important Hematology Values**

Hematology Variables	Units	Definition of Potentially Clinically Important Current (Version 4) Grade 3 or Greater	
		Very Low	
Hemoglobin	g/dL	< 8.0	
Platelets count	10  /L	< 50.0	
WBC count	10  /L	< 2.0	
Neutrophils	10  /L	< 1.0	
Lymphocytes	10  /L	< 0.5	

A separate listing will be provided that presents all of the subjects and values that are NCI CTCAE toxicity grade 3 or above. For each of these subjects, the whole course of the respective parameter will be listed. The NCI CTCAE grading is shown in [Table 10](#) below:

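### The SAP plans no by-arm laboratory count at the protocol's own WBC, platelet and 700/µl lymphocyte limits, and leaves eosinophils out of its laboratory variables

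*SAP*

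**What the plan says.** SAP 11.3.2 promises, under Potentially Clinically Important Laboratory Values: "Frequencies and percentages of subjects with post Baseline lab values meeting the following criteria will be summarized". Table 9 heads its haematology criteria "Definition of Potentially Clinically Important Current (Version 4) Grade 3 or Greater"; Table 8 does the same for chemistry. A by-subject listing covers grade 3 and above, with the grades set out in Table 10. Table 10 has no platelet row.

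Protocol 5.4.1.1 gives laboratory grounds for discontinuing FUMADERM:
- WBC below 3,000/µl, or a fall of more than 50% between two visits
- lymphocytes below 500/µl, or below 700/µl persisting 4 weeks after the dose is halved
- platelets below 100,000/µl
- "An increase in creatinine level above normal according to central laboratory normal range"

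Protocol 5.5.1 adds dose-reduction limits: lymphocytes below 700/µl, platelets from 100,000 to below 150,000/µl, and WBC from 3,000 to below 3,500/µl.

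On eosinophils, Protocol 3.2 states: "Leukocytopenia, lymphocytopenia, and eosinophilia are common side effects of fumaric acid esters". Protocol Table 3 lists the absolute eosinophil count. Section 5.3.1.1 has a CBC with differential at both complete and targeted laboratory visits. In SAP Table 7 the automatic differential holds neutrophils and lymphocytes only. SAP 14.1, which lists departures from the protocol, does not mention this.

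**The concern.** The study objective is to compare safety as well as efficacy. A table of potentially clinically important values is where a reader looks for the number of subjects per arm with a laboratory change that mattered. For WBC and platelets, the SAP's table starts counting only well past the point at which the protocol treats the value as a reason to stop the comparator. A subject with WBC 2.8 or platelets 90 × 10^9/L would meet a protocol limit without appearing in that table or in the grade 3 listing.

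For eosinophils, the protocol names an effect of the comparator and collects the data. It also plans, in 8.1.5, descriptive statistics and shift tables for laboratory data. The SAP's variable list then leaves the parameter out without saying so.

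**Working it through.** The plan has no calculated figure on this point, and the 94% power in Protocol 8.2 plays no part. The check is therefore a comparison of limits in common units (1,000/µl = 1.0 × 10^9/L).

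**Step 1: limits side by side.** Protocol limits come from 5.4.1, 5.4.1.1 and 5.5.1, and SAP limits from Tables 8 and 9. Blood counts are in 10^9/L.

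| Parameter | Protocol limit | SAP limit | SAP ÷ protocol | Range not counted |
|---|---|---|---|---|
| WBC | < 3.0 (stop) | < 2.0 | 2.0/3.0 = 0.67 | 2.0 to < 3.0 |
| Platelets | < 100 (stop) | < 50 | 50/100 = 0.50 | 50 to < 100 |
| Lymphocytes, single value | < 0.5 (stop) | < 0.5 | 1.00 | none |
| Lymphocytes | < 0.7 (reduce; stop if persistent) | < 0.5 | 0.5/0.7 = 0.71 | 0.5 to < 0.7 |
| Creatinine | > 1 × ULN (stop) | > 3 × ULN | 3.0 | > 1 to 3 × ULN |
| ALT/AST, single value | > 8 × ULN (stop, both arms) | > 5 × ULN | 5/8 = 0.63 | none; SAP limit is reached first |

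The > 50% WBC fall has no SAP counterpart. The WBC and platelet dose-reduction ranges in 5.5.1 also lie outside Table 9.

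**Step 2: which of these ranges do the other laboratory outputs recover?**
- Creatinine: yes. The limit is the upper end of the normal range, and Protocol exclusion 14 keeps out subjects above normal at screening. The shift from baseline to maximum value therefore counts the event itself.
- ALT/AST: yes. The protocol's combined rules start at > 3 × ULN. SAP 11.3.2 lists every subject with ALT or AST at or above 3 × ULN, and lists possible Hy's Law cases.
- WBC, platelets, lymphocytes below 0.7: no. Shift tables use low, normal and high. Exclusion 14 also bars any CBC parameter outside normal at screening, so most subjects should start as normal. A slight dip and a value at the protocol's limit then share the normal-to-low cell.
- Extreme-value statistics and listings in SAP 11.3 show individual values but give no number of subjects at a limit.
- The > 50% WBC fall: no. It needs pairs of visits, and no summary compares them.

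**Step 3: eosinophils through the SAP.** They are absent from Table 7 (variables), Table 9 (criteria) and Table 10 (grades). The protocol's hepatic withdrawal rule mentions eosinophilia above 5%, but only together with ALT or AST above 3 × ULN. Those subjects are already listed by enzyme value. Eosinophilia on its own has no clearly planned laboratory summary.

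**The case against.** The strongest reply is that a CTCAE grade 3 cut-off is openly labelled and applied alike to both arms. Discontinuation limits written for one drug serve a different purpose, and nothing in the documents requires the two to agree. That stands, and it is why Tables 8 and 9 should remain.

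The second reply is that these events are reported elsewhere. A laboratory abnormality that leads to discontinuation from the study is an adverse event by the protocol's definition. SAP 11.2.1 counts adverse events leading to discontinuation of study drug, tabulates them by SOC and PT, and lists them by subject. SAP 9.0 reports FUMADERM subjects who deviate from the dosing schedule, with reasons. This also largely stands. It does not give the laboratory comparison, for three reasons:
- The discontinuation and dose-reduction limits for blood counts apply to one arm.
- The adverse event definition does not name dose reduction, so a lymphocyte count of 650/µl handled by reducing the dose need not become an event.
- SAP 7.4 itself allows for subjects who meet withdrawal criteria and are not withdrawn.

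Third, SAP 11.3.2 says laboratory analyses follow the CTCAE scale, and grade 2 for WBC in Table 10 runs from < 3.0 to 2.0. A count by grade would close the WBC gap, but the SAP does not promise one; it ties Table 10 to the grade 3 listing. Nor would it help for platelets (no row) or match 700/µl (lymphocyte grade 2 begins below 0.8).

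Fourth, the shift tables are promised for each haematology parameter, which could be read to include eosinophils. Table 7 points the other way, so the text is at best ambiguous.

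**Conclusion.** The point holds in a narrow form. No planned output gives, for both arms, the number of subjects whose WBC, platelets or lymphocytes reached the limits in Protocol 5.4.1.1 and 5.5.1, apart from lymphocytes below 500/µl. No laboratory summary clearly covers eosinophils. The uncounted ranges are those in the table for WBC, platelets and lymphocytes, plus the > 50% WBC fall.

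A reader might infer more, and the documents do not support it:
- That the SAP's limits lie beyond the protocol's throughout. They coincide for single lymphocyte values, and the ALT/AST limit is the more sensitive of the two for a single value.
- That toxicity is missed or the comparator's harm under-reported. Adverse event tables, shift tables, extreme values and listings still show these events. What is absent is the frequency by arm.
- That the number of affected subjects can be stated. The protocol cites lymphopenia in 10.6% of FUMADERM subjects in an earlier trial, and 0.106 × 55 = 5.8. That figure carries no cell-count threshold, so it cannot be placed in the 0.5 to < 0.7 range. There is no comparable figure for WBC or platelets.

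The conclusion assumes that Table 7 defines the parameters to be summarised and that no grade 1–2 frequency table is intended. It is a cheap improvement to reporting, and it takes no view on where any clinical limit should lie.

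**What to change.** 1. Add absolute eosinophils to SAP Table 7, so that they receive the change-from-baseline and shift outputs already planned. If the omission is deliberate, record it with a reason in SAP 14.1.
2. Keep Tables 8 and 9. Add one table, with a by-subject listing, of the number and percentage of subjects in each arm with at least one post-baseline value meeting each WBC, platelet and lymphocyte limit already written in Protocol 5.4.1.1 and 5.5.1. Include the > 50% WBC fall, and state in the SAP which pairs of visits are compared. For 700/µl use the value alone, because persistence is defined relative to a FUMADERM dose reduction and has no counterpart in the other arm. Footnote that these limits were acted on in the FUMADERM arm only.
3. Add a platelet row to Table 10, on the CTCAE version that Table 9 already cites, so that the grade 3 listing plainly covers platelets.

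The cost is one table, one listing, one extra parameter and one extra row, all from central-laboratory data already collected. The downside is slightly more output. No clinical rule, visit or sample changes.

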### **3.0                   Introduction**

Psoriasis is a chronic inflammatory disease with raised, well-demarcated erythematous plaques with adherent silvery scales. It is the most prevalent immune mediated skin disease, affecting 2% of the world population. Twenty-five percent of patients have moderate to severe disease with considerable negative impact on psychosocial and economic status. It is increasingly recognized that psoriasis is more than a superficial disease, with 30% of patients having joint involvement and a high correlation between psoriasis and obesity, diabetes, depression, metabolic syndrome and cardiovascular risk.

While the majority of psoriasis patients are managed initially with topical therapies, those with severe and/or refractory disease may require phototherapy and/or systemic therapy. Oral systemic agents provide modest efficacy, but increasingly patients are treated with biological agents such as tumor necrosis factor (TNF)-alpha inhibitors (etanercept, adalimumab) and the interleukin (IL)-12/23 inhibitor (ustekinumab). While the clinical efficacy of ustekinumab indicates a role for both IL-12 and IL-23 in the pathogenesis of psoriasis, more recent data suggest that IL-23 is disproportionately involved in the maintenance of chronic psoriasis. IL-23 is thought to be involved in the pathophysiology of psoriasis via induction and maintenance of Th17 type cells, and other IL-23 responsive cells. This is supported by recent clinical data indicating that monoclonal antibodies (mAb) that block IL-17, the cytokine produced by Th17 cells, have high efficacy in psoriasis.

There is still clinical need for increased efficacy as the most effective anti-TNF and IL12/23 agents provide approximately 75% improvement in psoriasis in about 60 – 70% of patients and these responses tend to be lost over time. While the anti-IL-17 agents (i.e., secukinumab) may provide better efficacy, they require monthly injections, thus their long term utility is still undetermined.

Risankizumab is a fully humanized mAb of the IgG1 subclass directed towards IL-23p19. The antibody has been engineered to reduce Fc $\gamma$  receptor and complement binding and potential charge heterogeneity. Risankizumab binds with high affinity to human IL-23

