12. Any documented active or suspected malignancy or history of malignancy within 5 years prior to screening, except appropriately treated basal or squamous cell carcinoma of the skin or in situ carcinoma of uterine cervix.
13. Evidence of a current or previous disease, medical condition other than psoriasis, surgical procedure (i.e., organ transplant), medical examination finding (including vital signs and ECG), or laboratory value at the screening visit outside the reference range that in the opinion of the investigator is clinically significant and

---

would make the study participant unreliable to adhere to the protocol or to complete the study, compromise the safety of the patient, or compromise the quality of the data.

14. Subject has any condition or contraindication to FUMADERM® that would preclude the patient's participation in the present study, including, but not limited to:
  - A known hypersensitivity to fumaric acid derivatives or other components of FUMADERM® Initial or FUMADERM®
  - Any parameter of the CBC outside of normal range according to the central laboratory at Screening visit,
  - Severe liver disease (ALT or AST  $> 2 \times$  ULN according to central lab normal range, or total bilirubin  $> 1.5 \times$  ULN according to central laboratory normal range at Screening visit),
  - Severe kidney disease (serum creatinine above normal value according to central laboratory normal range at Screening visit),
  - Severe gastro-intestinal disease, such as a known active gastro-duodenal ulcer,
  - Inability to understand the complexity of FUMADERM® dosing regimen,
  - Any other exclusionary condition provided in FUMADERM® local label,
  - Any of the following risk factors for renal toxicity:
    - peripheral vascular disease
    - diabetes mellitus with microalbuminuria (UACR  $> 30$  mg/g) at Screening visit
    - Systolic blood pressure measurement of  $> 140$  mmHg or a diastolic blood pressure measurement of  $> 90$  mmHg at the Screening visit unless there is confirmation from an internist or a cardiologist that no renal or cardiovascular risk is associated with the elevated blood pressure.
    - History of congestive heart failure (NYHA Class III or IV)
15. History of allergy/hypersensitivity to any of the excipients in the risankizumab formulation.

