## **6.0 Analysis Conventions**

### **Definition of Baseline**

The last non-missing observation collected on or before the date of the first dose of study drug will be used as Baseline for summary of demographics and disease characteristics, safety and efficacy analyses.

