**Table 8. Criteria for Potentially Clinically Important Chemistry Values**

Chemistry Variables	Units	Definition of Potentially Clinically Important Current (Version 4) NCI CTCAE Grade 3 or Greater	
		Very Low	Very High
TBL	mcmol/L		> 3.0 × ULN
SGOT/AST	U/L		> 5.0 × ULN
SGPT/ALT	U/L		> 5.0 × ULN
Albumin	g/L	< 20	
Glucose	mmol/L	< 2.2	> 13.9
Triglycerides	mmol/L		> 5.7
Creatinine	mcmol/L		> 3.0 × ULN
Sodium	mmol/L	< 130	> 155
Potassium	mmol/L	< 3.0	> 6.0
Calcium	mmol/L	< 1.75	> 3.1
CPK	U/L		> 5.0 × ULN
Total Cholesterol	mmol/L		> 10.34
GGT			> 5.0 × ULN
ALP			> 5.0 × ULN

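### The counts of potentially clinically important laboratory values have no baseline condition, so a grade 3 value that was present before dosing and persists is counted as a post-baseline finding

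*SAP*

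**What the plan says.** **The count.** SAP 11.3.2, under Potentially Clinically Important Laboratory Values, states: "Frequencies and percentages of subjects with post Baseline lab values meeting the following criteria will be summarized". Table 8 heads its chemistry limits "Definition of Potentially Clinically Important Current (Version 4) NCI CTCAE Grade 3 or Greater" and Table 9 heads its hematology limits "Definition of Potentially Clinically Important Current (Version 4) Grade 3 or Greater". All are absolute values or multiples of ULN, and none refers to the subject's own starting value. SAP section 6.0 does define one: "The last non-missing observation collected on or before the date of the first dose of study drug will be used as Baseline".

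**Other laboratory outputs that use baseline.**
- SAP 11.3.2, Shift Tables: "Shift tables for changes from Baseline according to the normal range will be provided for each hematology and clinical chemistry parameter". The categories are low, normal, high and combinations of these, not toxicity grades.
- SAP 11.3.2, Liver Function Tests: shift tables in multiples of ULN, with a cut at 5.0, for ALT, AST, ALP and total bilirubin.
- SAP 11.3.2, below Table 9: a listing of every subject with a grade 3 or higher value, showing that parameter's full time course.

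**Entry limits.** Protocol 5.2.2, criterion 14, excludes "Any parameter of the CBC outside of normal range according to the central laboratory at Screening visit". It also excludes ALT or AST above 2 x ULN, total bilirubin above 1.5 x ULN and creatinine above normal. Criterion 13 excludes other out-of-range screening values only where the investigator judges them clinically significant and a threat to adherence, safety or data quality.

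**The concern.** A table of grade 3 laboratory values after baseline is normally read as showing what happened on treatment. Under the stated rule it mixes two groups: subjects who crossed the limit after dosing, and subjects who were already past it and stayed there.

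Glucose is the plainest route. The only diabetes-specific exclusion requires microalbuminuria, no numeric glucose limit is set at entry, and Protocol section 3.0 describes "a high correlation between psoriasis and obesity, diabetes, depression, metabolic syndrome and cardiovascular risk". A subject who enters with glucose above 13.9 mmol/L and remains there is counted.

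Comparing safety is part of the study objective. If grade 3 counts are small, as is likely with 55 subjects per arm, one or two carried-over cases could mask a real difference in a parameter or produce one that neither drug caused.

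**Working it through.** The plan states no figure for this point, so there is nothing to reproduce. The check is a row count of the tables, followed by an illustration of scale.

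**Step 1. Which parameters are exposed?** Tables 8 and 9 hold 14 + 5 = 19 parameters, with 23 low or high limits in all.

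| Group | Parameters | Number |
|---|---|---|
| Numeric entry limit at Screening rules out grade 3 | Total bilirubin, AST, ALT, creatinine, hemoglobin, platelets, WBC, neutrophils, lymphocytes | 9 |
| Sampled at Screening only (SAP Table 7, footnote a) | Triglycerides, total cholesterol | 2 |
| No numeric entry limit, post-baseline samples scheduled | Albumin, glucose, sodium, potassium, calcium, CPK, GGT, ALP | 8 |

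19 - 9 - 2 = 8 parameters, carrying 12 of the 23 limits. Two qualifications apply to the first group. Eligibility is judged at Screening but baseline may be the Day 1 sample, so a grade 3 baseline is unlikely rather than impossible. Neutrophils and lymphocytes belong there only if CBC includes the differential, as the wording of Protocol 5.3.1.1 on targeted laboratory tests suggests.

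**Step 2. Do the other outputs separate old from new?**
- ALP: yes. The ULN-multiple shift table has a cut at 5.0, which is the Table 8 limit apart from at-or-above versus above.
- The other seven: no summary table does. In the normal-range shift table, a baseline just above normal that rises to grade 3 and a grade 3 value that never moved both appear as high to high.
- The listing shows each case's baseline but leaves the by-arm number and percentage unchanged. I assume it covers albumin, glucose, sodium, potassium and calcium through their Table 8 limits, because Table 10 gives them no grades.

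**Step 3. Scale.** One carried-over subject adds 1/55 = 1.8 percentage points to an arm.

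Let b be the proportion of subjects with a persisting baseline grade 3 value in a given parameter. The documents give no value, so b is an assumption. With X1 and X2 independent Binomial(55, b):
- expected carry-over per arm and parameter = 55 x b
- d = P(|X1 - X2| ≥ 2)
- chance of such a difference in at least one of eight independent parameters = 1 - (1 - d)^8

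| b | 55 x b | d | 1 - (1 - d)^8 |
|---|---|---|---|
| 0.1% | 0.06 | 0.003 | 2% |
| 0.2% | 0.11 | 0.010 | 8% |
| 0.5% | 0.28 | 0.048 | 33% |
| 1% | 0.55 | 0.133 | 68% |
| 2% | 1.10 | 0.281 | 93% |

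With seven parameters (ALP set aside) the last column is 29%, 63% and 90% at b = 0.5%, 1% and 2%. The 2% row is hard to believe as a uniform rate: 1 - 0.98^8 = 15% of subjects would enter with at least one persisting grade 3 value.

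**The case against.** The strongest reply is that baseline is missing from one descriptive count, not from the laboratory reporting. If the counts are small, a reader can open the listing and check each case. The text calls these values post-baseline rather than new or treatment-emergent. No test, endpoint or decision rule uses them. Criterion 13 gives the investigator a way to exclude a worrying screening value in any of the eight parameters. All of this stands and limits the importance of the point. It does not make the by-arm percentages right: the listing needs case-by-case reconstruction, and criterion 13 sets no number.

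Several stronger readings are tempting but not supported:
- *Every grade 3 value before dosing is counted.* It is counted only if a post-baseline value also meets the limit; an abnormality that resolves drops out.
- *The comparison is biased towards one arm.* Randomization balances pre-existing abnormalities in expectation.
- *The SAP already accepts a baseline condition elsewhere.* In Table 11 only systolic pressure needs both a limit and a change. Diastolic pressure and pulse join the two with or, so an absolute value alone qualifies.
- *The protocol shows that diabetes will be frequent in this sample.* It asserts a correlation and gives no prevalence.
- *The 33% and 68% figures are forecasts.* They apply one assumed rate to parameters as different as glucose and albumin below 20 g/L, and they fall to about 2% at a rate of 0.1%.

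**Conclusion.** The point holds within limits. The rule in SAP 11.3.2 counts a persisting pre-dose grade 3 value as a post-baseline finding. Seven parameters are exposed with no summary table that separates old from new (albumin, glucose, sodium, potassium, calcium, CPK, GGT). An eighth, ALP, is exposed in the count but recoverable. The consequence is inflated percentages and added chance variation in a descriptive safety table, at 1.8 percentage points per carried-over subject if an arm of the Safety Population has 55 subjects. The total size cannot be fixed from the documents. The chance of a two-subject imbalance in at least one of the eight parameters runs from about 2% to 68% for assumed prevalences of 0.1% to 1%, given persistence, independence and a common rate. The primary analysis is untouched. The change is worth making because it is cheap and uses data already collected.

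**What to change.** In SAP 11.3.2, replace the counting sentence with a rule of this form: a subject is counted for a Table 8 or Table 9 limit when at least one post-baseline value meets that limit and the baseline value did not meet it, or baseline is missing. Apply it to low and high limits separately. Add a row, by arm, for subjects who already met the limit at Baseline. Keep the grade 3 listing unchanged.

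The condition should test the Table 8 or 9 limit rather than a rise in toxicity grade. Table 10 has no grades for albumin, glucose, sodium, potassium or calcium, so a grade-based rule could not be run for five of the eight exposed parameters.

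The cost is one sentence, one condition in the program and one extra table row, with no new data. Headline counts become slightly smaller. A subject who worsens from grade 3 to grade 4 would appear in the separate row and the listing, not in the main count.
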